
The following aims and hypotheses will be addressed in this proposal.

Specific Aim 1: To identify impairments in neural systems underlying comorbid AUD/ET by examining fMRI response during a dynamic SEP task

Hypothesis: Ventromedial prefrontal cortex (VmPFC) (stress-baseline). The AUD/ET group will display a lack of dynamic VmPFC response in the Late-Stress period.

Hypothesis 1b: Ventral Striatum (VS) (alcohol cue-baseline). The AUD/ET group will show decreased VS activity during alcohol cue exposure, while AUD/NT group show increased VS response to alcohol cue.

Specific Aim 2: To evaluate neural correlates of HPA axis response using a validated fMRI and HPA approach

Hypothesis 2. Lower dynamic VmPFC response to stress will be associated with blunted cortisol response to stress (stress-baseline) across groups.

Specific Aim 3: To examine whether impaired neural responses during the SEP task predict future relapse after treatment during the 90-day follow-up

Hypothesis 3. Lower dynamic VmPFC response to stress will predict early relapse.

2. Probable Duration of Project:

Duration of the project: 5 years (recruiting 160 participants)

A total of 160 subjects (ages 21-50) will be recruited including four demographically-matched groups (N=40 each; equal sex ratio) of 80 treatment-seeking AUD patients with and without early trauma (AUD/ET, AUD/NT) and 80 moderately drinking controls with and without early trauma (MD/ET, MD/NT). An experiment is proposed using a 2 (AUD, MD) X 2 (ET, NT) x 3 (Condition: Stress, Alcohol, and Neutral) mixed factorial design with the first two factors (Groups) as between-subjects factors and Condition as a within-subjects factor. Equal genders will be included in each group, and the effects of gender will be assessed. All AUD patients will be scheduled for a multimodal fMRI scan during acute abstinence within 3-5 days of last drink. Then patients will receive an 8-week outpatient treatment and scheduled for a second scan in the 8th week of the treatment. Moderate drinking controls will participate in a single MRI session after baseline assessments.

Duration of study participation:

AUD patients: 22 weeks (baseline/MRI session (2 weeks), outpatient treatment (8 weeks) + follow-up (12 weeks))

Control subjects: 6 weeks (baseline/MRI session (2 weeks), follow-up (4 weeks))

3. Background:

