AUD patients will complete MRI sessions before and after 8-week outpatient treatment. After the MRI session, AUD subjects will receive an outpatient treatment integrating cognitive-behavioral methods focused on emotion regulation with breathing-based stress management. This program partly adapts the Cognitive Behavioral Relapse Prevention supported by NIAAA manual [16] and resonance breathing techniques. During an 8-week outpatient treatment, participants will also receive two smartphone surveys including a 56-day daily monitoring survey and a 56-day daily intervention exercise. A 56-daily monitoring survey will assess daily stress and alcohol consumption in a real-life setting, and a 56-day intervention exercise will provide breathing exercise instruction with a couple questions asking their experience practicing breathing techniques. After the second MRI session, AUD patients will be engaged in a prospective follow-up, combining conventional interviews with daily monitoring via smartphone app. Subject will also have the option for a 90-day follow-up interview remotely via phone or zoom meeting. Face-to-face or remote follow-up via phone or zoom meeting interviews will be conducted at days 14, 30, and 90 days as described

previously [15,19,20]. In addition, to accurately capture relapse rate, AUD patients will be tracked once daily to monitor their stress, emotion, and alcohol use through a smartphone app technique for 90 days. Then, participants will be scheduled to visit the Stress Center for a 90-day follow-up interview or to have a remote session and will be debriefed. .

Moderate drinkers with and without early trauma (MD/ET, MD/NT)

After the MRI session, all participants will be tracked for 30 days to monitor their stress, emotion, and alcohol use through the same smartphone app technique.

Assessments

All participants will be assessed across the following domains, using psychometrically established measures.

The Structured Clinical Interview for DSM-V (SCID-I) will be used to ascertain DSM-5 Axis 1 psychiatric and substance abuse diagnoses [21] and specifically to determine presence/absence of DSM-5 AUD.

Assessment for Alcohol use and addiction:

Family history of alcoholism (FH) will be assessed using the Family Tree Questionnaire [22]; [23] which provides a method to obtain drinking status and alcohol-related problems for all maternal and paternal first and second degree relatives above the age of 18.

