Aim 2: neural correlates of HPA axis function: For basal cortisol levels, a 2×2 factorial design will be applied with AUD (AUD, MD) and ET (ET, NT) as the between-subjects factors. For changes in stress hormone (cortisol, ACTH) during the SEP task, all data analyses will use change from baseline (provocation minus baseline) values. Then, a $2 \times 2 \times 3$ mixed-factorial design will be used with AUD (AUD, MD) and ET (ET, NT) as the between-subjects factors and Condition (Alcohol, Stress, Neutral) as the within-subjects factors. In addition, to examine the associations between task-related brain activity and stress hormone response, whole-brain correlation analyses will be conducted using BioImageSuite.

Aim 3: neural correlates of relapse: As reported in our previous papers [15,19,20], the primary outcome of relapse and treatment will be time to relapse (event based) and secondary outcome will be percent days of alcohol use during the follow-up period. These measures will also be assessed for their sensitivity and specificity of relapse risk prediction and treatment outcome over and above clinical and demographic measures associated with relapse and treatment outcome. For event-based relapse outcome measures (time to relapse, time to heavy drinking relapse), Cox proportional hazards regression (PHREG) models will be implemented for the primary predictor variable of dynamic VmPFC response controlling for any significant clinical, alcohol history or demographic measures that predict relapse [15,20].

SECTION II: RESEARCH INVOLVING DRUGS, BIOLOGICS, RADIOTRACERS, PLACEBOS AND DEVICES

If this section (or one of its parts, A or B) is not applicable, check off N/A and delete the rest of the section.

A. RADIOTRACERS **N/A**

1. Name of the radiotracer: *Write here*
2. Is the radiotracer FDA approved? **YES** **NO**

If NO, an FDA issued IND is required for the investigational use unless RDRC assumes oversight.

9. Check one: IND# *Write here* or RDRC oversight (RDRC approval will be required prior to use)
4. **Background Information:** Provide a description of previous human use, known risks, and data addressing dosage(s), interval(s), route(s) of administration, and any other factors that might influence risks. If this is the first time this radiotracer is being administered to humans, include relevant data on animal models.
Write here
4. **Source:** Identify the source of the radiotracer to be used. *Write here*

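### Aim 3 plans relapse sensitivity and specificity in at most 80 AUD patients with no internal validation, so on the likely reading whole-model accuracy will on average be too high

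*Combined protocol and SAP*

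**What the plan says.** Specific Aim 3 asks whether neural responses "predict future relapse after treatment during the 90-day follow-up", and Hypothesis 3 reads "Lower dynamic VmPFC response to stress will predict early relapse". Section 13, Aim 3, makes time to relapse the primary outcome and fits a Cox model for the "primary predictor variable of dynamic VmPFC response". The adjustment rule is given as "controlling for any significant clinical, alcohol history or demographic measures that predict relapse", and two of the group's earlier papers are cited for this. The section also says: "These measures will also be assessed for their sensitivity and specificity of relapse risk prediction". The same sentence extends this to how treatment turns out, and it sets the standard of comparison as "over and above clinical and demographic measures associated with relapse and treatment outcome".

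Only the two AUD groups have the 90-day relapse follow-up: 2 x 40 = 80 patients. Attrition is not allowed for, although section 10 permits withdrawal.

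No section gives a covariate list, a screening threshold, a cut-off rule, a hold-out sample, cross-validation, bootstrap or shrinkage. Where the opening summary and Aim 2 call an approach validated, they mean the imaging and hormone technique, not a prediction model.

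Section 4 says "AUD patients will complete MRI sessions before and after 8-week outpatient treatment". The relapse analysis does not name the scan that supplies the predictor.

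**The concern.** If covariates are kept because they are significant in these patients, the model is fitted to the same patients, and its accuracy is then scored on them, the accuracy absorbs chance features of the sample. With 80 or fewer patients and a long battery of instruments (section 4, Assessments), that optimism need not be small.

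The opening summary puts VmPFC response forward as a predictor of high relapse risk. Readers would take the sensitivity and specificity as evidence of how well relapse can be classified, and the increment over clinical measures as evidence of what imaging adds. Uncorrected, the first is too favourable on average and the second is unreliable in either direction.

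**Working it through.** The plan gives no accuracy, event-count or power figure to reproduce. The check is by simulation.

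**From the documents.** At most 80 AUD patients; 90-day horizon; Cox model; covariates kept if significant; VmPFC always in the model.

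**Assumed (not in the documents).** 60 or 80 patients with complete follow-up; 50% or 60% relapse (80 x 0.50 = 40 relapses, 60 x 0.50 = 30); screening at p<0.05; 10 independent candidates, or 6 correlated at 0.5; three or none prognostic (log HR per SD 0.40, or 0.283 if correlated); VmPFC HR per SD of 1.0, 1.3, 1.5 or 1.8.

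**Steps.**
1. Draw exponential relapse times with hazard proportional to exp(linear predictor), censored at day 90.
2. Screen each candidate in a one-variable Cox model, then refit the retained covariates plus VmPFC.
3. Optimism = accuracy in the sample - accuracy of the same fitted model in 4,000 new patients.
4. Gain = AUC(covariates + VmPFC) - AUC(covariates).

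**Whole model.** In all 64 settings the mean AUC was too high: by 0.037-0.108 with three prognostic candidates and by 0.013-0.116 with noise candidates. With three prognostic candidates and the cut-off also chosen in the sample, sensitivity + specificity was 0.15-0.27 too high.

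A second simulation under different assumptions agrees (n = 80, 60% relapse, 20 candidates with two prognostic, VmPFC log HR 0.4):
- AUC 0.777 in sample against 0.691 in new patients: 0.777 - 0.691 = 0.086.
- Sensitivity 0.71 against 0.62 and specificity 0.77 against 0.64: (0.71 + 0.77) - (0.62 + 0.64) = 0.22.
- With 10 candidates, AUC 0.760 against 0.705, a difference of 0.055.
- Across its scenarios, in-sample AUC exceeded the new-patient AUC in 77-98% of runs. This is a statement about averages, not about every data set.

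**VmPFC alone.** With no covariates fitted and the direction taken as hypothesised, only the choice of cut-off is optimistic: sensitivity + specificity is about 0.11-0.15 too high (60-80 patients, 50% relapse).

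**Gain from VmPFC, measure fixed in advance.**

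| HR per SD | Bias in AUC gain |
|---|---|
| 1.0 | +0.011 to +0.048 |
| 1.3 | -0.003 to +0.014 |
| 1.5 | -0.019 to +0.004 |
| 1.8 | -0.032 to -0.002 |

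For scale, the HR detectable with 80% power at two-sided 5% is exp((1.96 + 0.84)/√D) for D relapses. D = 40 gives exp(2.80/6.32) = 1.56; D = 56 gives exp(2.80/7.48) = 1.45.

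**Primary Cox test.** In the second simulation, with no VmPFC effect, it rejected in 4-9% of runs at nominal 5%. With a true coefficient of 0.40, the mean estimate was 0.38-0.42.

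**Does correction work?** Corrected value = in-sample value - mean over resamples of (accuracy in the resample - accuracy of the resample's model in the original data). For n = 80, 20 candidates and 60% relapse:

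| AUC | No VmPFC effect | VmPFC log HR 0.4 |
|---|---|---|
| In sample | 0.754 | 0.780 |
| New patients | 0.649 | 0.697 |
| Corrected, screen repeated | 0.654 | 0.693 |
| Corrected, screen not repeated | 0.724 | 0.759 |

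Without repeating the screen, 0.724 - 0.649 = 0.075 of the original 0.754 - 0.649 = 0.105 remains in the first column.

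**The case against.** The analysis at issue is partly inferred. The subject of the accuracy sentence is, grammatically, the outcomes, and it names neither a combined model nor a cut-off. An outcome cannot predict relapse beyond clinical measures, so a prediction based on VmPFC is presumably meant. If that is VmPFC alone, the whole-model optimism falls away and only the cut-off optimism stands.

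The covariate sentence cites earlier papers, so its covariates may come from them rather than from a screen of this sample. That cannot be checked here. It would shrink the problem but not remove it: with two prognostic covariates fixed in advance, AUC was still 0.776 in sample against 0.742 in new patients.

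A reader might infer that the VmPFC version or scan will be picked by how well it predicts relapse. The documents do not support this. Hypothesis 3 specifies response to stress. Aim 1 gives a stress-minus-baseline contrast and expects a "lack of dynamic VmPFC response in the Late-Stress period". The opening summary and the end of section 3 place treatment and follow-up after the imaging, which points to the pre-treatment scan. No section plans a choice based on relapse data. What stands is that the relapse model does not name the scan.

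The sizes rest on assumed relapse rates, candidate counts and effects. The direction for whole-model accuracy did not change in any setting tried.

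**Conclusion.** The concern holds for the accuracy figures. On the likely reading (in-sample screening plus a combined model), following the plan as written gives a whole-model AUC about 0.04-0.11 too high on average, and sensitivity plus specificity about 0.15-0.27 too high with a data-chosen cut-off. This is under the stated assumptions with three prognostic candidates. If VmPFC is assessed alone, the excess is about 0.11-0.15 and comes from the cut-off only.

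Two stronger conclusions do not follow. A reader might infer that the increment credited to VmPFC is always inflated. It is inflated if VmPFC has no effect, about unbiased at a moderate effect and understated at a strong one. A reader might also infer that the Hypothesis 3 test is compromised; it is largely unaffected.

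This is a cheap improvement to a secondary claim that should be made. It is not a defect in the primary analysis.

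**What to change.** 1. Report day-90 sensitivity, specificity and AUC (allowing for censoring), and the gain from adding VmPFC, as bootstrap optimism-corrected values with intervals. Repeat covariate screening, model fitting and any cut-off choice in each resample.
2. Base any statement of value beyond clinical measures on the corrected gain and its interval, and say which measures the accuracy sentence refers to.
3. Preferably replace the screen with a short clinical comparator fixed in advance from data already collected.
4. State that the VmPFC stress-minus-baseline measure comes from one named scan.

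**Cost.** SAP wording and some code; no new data. The accuracy figures will look less favourable.

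Item 3 is a preference, because the bootstrap alone removes most of the whole-model optimism. A fixed comparator may omit a real predictor. Compared with screening, its new-patient AUC was 0.045-0.075 higher if all three covariates were prognostic and 0.005-0.023 higher if two were. If none were and VmPFC had an effect, it was 0.006-0.013 lower.

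Correction is not complete. With two or three prognostic fixed covariates, corrected AUC was within -0.002 to +0.011 of the new-patient value and the gain within -0.009 to +0.007. With three that are not prognostic, AUC stayed up to 0.044 too high and the gain up to 0.029 too low. Sensitivity + specificity at a data-chosen cut-off stayed 0.03-0.06 too high even with two or three real covariates, which favours fixing the cut-off in advance.

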Early trauma (ET) is a significant obstacle to alcohol recovery. Among treatment-seeking alcohol use disorder (AUD) patients, 55% reported a history of early trauma [1]. AUD patients with ET suffer from more severe clinical symptoms and worse treatment outcomes including frequent and early relapse compared to those with AUD alone [2]. Yet, there is no established model explaining neural mechanisms of AUD, early trauma and high relapse risk. Two systems are implicated in the neurobiology of alcoholism and early trauma: stress-related neural circuits and the hypothalamic–pituitary–adrenal (HPA) axis response. However, studies concurrently examining these two systems are rare, and specific neurobiological mechanisms underlying co-occurring AUD and ET remain unclear. The current research proposes to investigate neurobiological mechanisms of comorbid AUD and ET and their prospective prediction of alcohol relapse using a multimodal neuroimaging technique that combines functional magnetic resonance imaging (fMRI) and HPA axis measures. Our novel, validated approach that allowed simultaneous monitoring of brain and hormone responses found dynamic neurobiological responses to stress during a sustained emotion provocation (SEP) task [3]. New preliminary results in AUD patients with ET showed altered response in the ventromedial prefrontal cortex (VmPFC) and ventral striatum during the SEP task. Specifically, poor dynamic VmPFC recovery over time predicted blunted cortisol response during stress and early relapse in AUD patients, suggesting the crucial role of dynamic VmPFC response in HPA axis disruption and relapse risk. These preliminary data led us to hypothesize that disrupted neural response in the VmPFC during the SEP task may be a novel marker to identify AUD patients with early trauma, and that impaired VmPFC dynamic response is a predictor of HPA axis disruption and high relapse risk in AUD patients. Accordingly, we propose a 5-year study with four demographically-matched groups (total N=160; N=40 each; equal gender) categorized by AUD and early trauma status, including AUD patients with and without early trauma (AUD/ET, AUD/NT), and moderate social drinkers with and without early trauma (MD/ET, MD/NT). The proposed study will utilize our novel SEP task involving exposure to stress, alcohol, and neutral cues in separate blocks, which fMRI and stress hormone monitoring via concurrent blood collection, combined with a prospective clinical outcome design. After the multimodal scan, AUD patients will be engaged in 8-week alcohol treatment and then prospectively followed for 90 days. To accurately capture relapse rate, we will utilize face-to-face follow-up interviews at 14, 30, 90 days as used in our previous work, in conjunction with daily monitoring of stress and alcohol use through a smartphone app.

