AUD patients with ET suffer from more severe clinical symptoms and worse treatment outcomes including frequent relapse compared to those with AUD alone [2]. We have shown that early trauma is a critical predictor of addiction relapse including AUD [4]. Especially, AUD patients with ET are known to be more vulnerable to stress-induced alcohol relapse [5,6]. Although multiple studies have consistently found a strong association between early trauma and increased risk of relapse among AUD patients, there is no previous neurobiological research examining the link between AUD, ET, and high relapse risk. Two stress-related systems have been implicated in the neurobiology of AUD and ET: stress-related prefrontal-limbic-striatal circuits and the hypothalamic-pituitary-adrenal (HPA) axis system. The HPA axis plays a crucial role in associating childhood trauma with alcohol drinking behaviors [7]. Stress responses involve HPA axis arousal [6], whereby glucocorticoids trigger increased dopamine efflux in the prefrontal cortex (PFC), resulting in prefrontal regulatory dysfunction under stress [8]. Early stressors result in long-term alterations in cortisol response and dopamine reward pathways in the brain, enhancing the reinforcing effects of alcohol [7,9]. The HPA axis function is modulated by the ventromedial prefrontal cortex (VmPFC), which plays a key role in controlling emotion, reward, and decision-making [10,11]. VmPFC dysfunction has been reliably associated with greater emotional distress in individuals experiencing high levels of stress and trauma [12], those with PTSD [13], and with high alcohol craving and early relapse in AUD patients [14,15]. These results point to the potential role of the VmPFC linking stress, alcohol consumption, and HPA axis dysfunction in patients with comorbid AUD/ET. However, no study has simultaneously examined these two systems.

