For the current study, the following individuals, funding, and/or regulatory agencies will be notified:

- All Co-Investigators listed on the protocol.
- Yale Cancer Center Data and Safety Monitoring Committee (DSMC)
- National Institutes of Health (National Institute on Alcohol Abuse and Alcoholism)
- Food and Drug Administration (Physician-Sponsored IND #_____)

- Medical Research Foundation (Grant _____)
- Study Sponsor
- Other Data Safety Monitoring Board (DSMB) or Committee (DSMC)

The principal investigator will conduct a review of all adverse events upon completion of every study subject. The principal investigator will evaluate the frequency and severity of the adverse events and determine if modifications to the protocol or consent form are required.

13. Statistical Considerations: Describe the statistical analyses that support the study design.

Procedures for data management will follow the YSC and Yale MRRC procedure, and we will use Research Electronic Data Capture (REDCap), a HIPPA compliant, secure web application. The data analytic plan described below focuses on testing the specific hypotheses in the Aims section.

Behavioral Data Analysis: fMRI task ratings (stress, craving) will be analyzed using linear mixed models, with two groups (AUD, ET) as between-subjects factors and Condition (Alcohol, Stress, Neutral) as within-subjects factors.

Analysis of Stress Hormone: For plasma samples, assay processing will be conducted using standard radioimmunoassay procedures used in our prior work [3,20] at the Core Laboratory of the Yale Center for Clinical Investigation. We will also assess maximal or peak response and area under the curve for each measure, which are commonly used in the literature (e.g., [20]).

Analysis of HRV and Eye Tracking: HR and HRV data will be processed and analyzed using MATLAB and Kubios HRV software. For HRV, the root mean square of successive differences (RMSSD) will be calculated from beat-to-beat intervals. Eye tracking data will be analyzed using R and MATLAB. Position changes of the eye in the X-Y plane will be recorded, and fixation location, duration and count will be calculated during picture viewing.

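### Early trauma splits the AUD patients 40/40 but has no guaranteed term in the relapse models, and no AUD/ET versus AUD/NT relapse comparison is prespecified

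*Combined protocol and SAP*

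**What the plan says.** The opening summary sets out to "investigate neurobiological mechanisms of comorbid AUD and ET and their prospective prediction of alcohol relapse" and describes four groups ("total N=160; N=40 each; equal gender"), so the AUD arm is 40 AUD/ET and 40 AUD/NT. All AUD patients are followed for relapse for 90 days after treatment. Section 3 (Background) gives the gap to be filled as: "there is no previous neurobiological research examining the link between AUD, ET, and high relapse risk".

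In 13. Statistical Considerations, ET group is a named factor in the models for task ratings, for imaging (Aim 1) and for basal and task-related hormones (Aim 2). For relapse (Aim 3) it is not named. Time to relapse and time to heavy-drinking relapse go into Cox models for the "primary predictor variable of dynamic VmPFC response controlling for any significant clinical, alcohol history or demographic measures that predict relapse". A second Aim 3 sentence plans sensitivity and specificity for predicting relapse beyond those clinical and demographic measures that are themselves associated with it. That sentence does not name ET either, and it carries the same kind of condition.

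The Aim 1 hypothesis on VmPFC reads: "The AUD/ET group will display a lack of dynamic VmPFC response in the Late-Stress period". The opening summary also says that AUD patients with ET relapse more often and earlier than those with AUD alone.

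**The concern.** ET is the factor by which the AUD patients are sampled, yet its place in the relapse analysis depends on two unstated decisions: whether it is a candidate covariate at all, and what level of significance keeps it in.

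Two things are at stake. First, the plan guarantees no hazard ratio for AUD/ET versus AUD/NT, and one that appears only after passing a significance screen is a selected estimate. Second, the protocol's own expectations make ET a likely confounder of the association between VmPFC response and relapse: it precedes both, and is expected to weaken the first and hasten the second. If ET is left out, part of a VmPFC hazard ratio could reflect trauma group.

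**Working it through.** The documents give no power calculation, relapse rate, dropout, effect size, Cox alpha or screening threshold, so there is no figure of the plan's to reproduce beyond 4 x 40 = 160 and 2 x 40 = 80, which agree.

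**Inputs.** From the documents: 80 AUD patients, 1:1 by ET, 90-day follow-up. Assumed: relapse 60% (range 40-80%), all 80 evaluable (or 60), two-sided 0.05 for both the test and the screen, true ET hazard ratio (HR) 1.5 or 2.0, and VmPFC response lower in ET by 0.5-1.0 within-group SD.

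**1. Chance that ET survives the screen.** With 1:1 groups, z = ln(HR) x sqrt(events)/2, and P(kept) is about Phi(z - 1.96). Events = 0.60 x 80 = 48.
- HR 1.5: z = 0.405 x 6.928/2 = 1.40; kept 29%, dropped 71%.
- HR 2.0: z = 0.693 x 6.928/2 = 2.40; kept 67%, dropped 33%.
- Over 40-80% relapse (32-64 events), ET is dropped 63-79% of the time at HR 1.5 and 21-50% at HR 2.0.

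**2. Selection of the ET estimate.** The SE of ln(HR) is 2/sqrt(48) = 0.289. In the expected direction the smallest HR kept is exp(1.96 x 0.289) = 1.76. If the true HR is 1.5, the mean retained ln(HR) is 0.405 + 0.289 x 1.18 = 0.747, an HR of about 2.1 (normal approximation; 1.18 is the normal density divided by the upper-tail area at (0.566 - 0.405)/0.289 = 0.555).

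**3. Effect on the VmPFC test.** Simulation with 4,000 data sets per row, 40 ET and 40 NT, exponential relapse times censored at day 90, about 48 events, and no true VmPFC effect. Entries in the last three columns are VmPFC type I error.

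| ET HR | VmPFC difference (SD) | ET enters | ET screened | ET always in | ET never in |
|---|---|---|---|---|---|
| 1.5 | 0.5 | 28.4% | 5.5% | 5.1% | 7.1% |
| 1.5 | 0.8 | 27.4% | 5.9% | 5.6% | 8.5% |
| 2.0 | 0.5 | 65.7% | 5.7% | 5.6% | 9.2% |
| 2.0 | 0.8 | 65.5% | 5.8% | 5.3% | 14.9% |
| 2.0 | 1.0 | 66.8% | 6.2% | 5.0% | 19.0% |

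The Monte Carlo SE near 5% is sqrt(0.05 x 0.95/4000) = 0.34 percentage points. Under screening the average VmPFC HR is 1.02-1.04 instead of 1.00.

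**4. What a fixed ET term can deliver.** The ET HR detectable with 80% power is exp(2 x (1.96 + 0.842)/sqrt(events)). For 32/40/48/56/64 events (80 evaluable) it is 2.69/2.43/2.25/2.11/2.01. With 60 evaluable it runs from 3.14 down to 2.25. Power with 80 evaluable is 21-37% at HR 1.5 and 50-79% at HR 2.0.

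**5. What it costs the VmPFC estimate.** The detectable HR per SD is exp(2.802/sqrt(48 x (1 - R2))), where R2 is the share of VmPFC variance explained by ET. It is 1.50 at R2 = 0 and 1.53, 1.57 and 1.62 at R2 = 0.1, 0.2 and 0.3. A group difference of d SD gives R2 = d²/(d² + 4), so 0.5-1.0 SD corresponds to 0.06-0.20.

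**The case against.** The analysis plan says what it is for: "The data analytic plan described below focuses on testing the specific hypotheses in the Aims section". The relapse hypothesis is about VmPFC alone: "Hypothesis 3. Lower dynamic VmPFC response to stress will predict early relapse". Section 3 treats the link between trauma and relapse as already shown and places the gap in neurobiology. The trauma questionnaire belongs to the assessment battery, so ET can fairly be read as a clinical measure. If it passes the screen, the planned model does test VmPFC adjusted for ET, and the incremental-prediction sentence bears on the same question. Operating the screen also means estimating ET's association with relapse, so dropping ET from the final model does not by itself mean that it goes unreported. Details of the covariate rule may lie in the cited earlier papers, which are not available here.

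Most of this stands, and it rules out three stronger readings that a reader might infer.
- That the trial cannot say how trauma relates to relapse. The 40/40 split and the follow-up supply the data; what is missing is a prespecified analysis.
- That the trial fails to show whether trauma drives relapse. ET is observed, not randomised, and its effect on relapse is not a stated hypothesis. No model here could show more than association.
- That a significant VmPFC result would probably be a stand-in for trauma. That needs ET to be excluded altogether; under a p<0.05 screen the type I error is close to that with ET forced in.

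What the objection does not remove is that nothing in Aim 3 guarantees an ET term or contrast, although the stated objective concerns comorbid AUD/ET and relapse.

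**Conclusion.** The gap is real and worth closing, but it is one of prespecification and does not defeat Aim 3. Under the assumed 48 events, a screen at p<0.05 would leave out a true ET hazard ratio of 1.5 about 71% of the time and one of 2.0 about 33% of the time, and any estimate that it kept would be biased away from 1 by selection. The VmPFC test is materially affected (about 7-19% type I error in the scenarios run) only on the reading that ET is not a candidate covariate; on the other reading it stays near 5.5-6.2%. The text does not say which reading applies. All of these figures rest on assumed relapse rate, follow-up, alpha and effect sizes. The absence of a guaranteed ET term does not.

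**What to change.** In Aim 3, include ET group (ET/NT) as a fixed term, whatever its p-value, in the Cox models for time to relapse and time to heavy-drinking relapse and in the model for percent drinking days. For the Cox models, report in order:
1. the AUD/ET versus AUD/NT hazard ratio with its confidence interval, without VmPFC;
2. the ET and VmPFC hazard ratios from one model;
3. the VmPFC x ET interaction, labelled exploratory.

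Use the same sequence of terms for percent drinking days, and state that ET is interpreted as an association, not a cause. Other covariates can stay under the existing rule as far as this point is concerned.

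The cost is a short addition to the text, one degree of freedom per model (a second for the exploratory interaction) and no new data. The VmPFC estimate becomes slightly less precise. In simulation with a true VmPFC HR of 1.5 per SD and a 0.8 SD group difference, power is 73.0% with ET forced in against 76.1% with ET screened when the ET HR is 1.5, and 71.7% against 73.0% when it is 2.0. The ET comparison itself will be imprecise (detectable HR about 2.0-2.7 with 80 evaluable patients and 40-80% relapse), so it should be presented as an estimate with its interval and not judged by significance. The change should be made before the relapse data are examined; afterwards the comparison would be post hoc.
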